### **GOALS:**

- **Main objective**

The measurement of pain intensity according to the NRS at different times: preoperative and at the 1st, 2nd, 12th and 24th postoperative hours.

- **Secondary objectives**

Postoperative opioid consumption and comparison of total cumulative consumption between the two groups.

It will also evaluated the degree of sensory and motor block, the easy of performance of the anesthetic technique, the degree of patient satisfaction and the record of short-term complications (first 24 hours post-intervention): hematoma, pruritus, nausea and/or vomiting.

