## **STUDY TYPE**

An observational study of paired cohorts, not randomized, is designed in two hospitals in northern Spain in the period between october 2023 and september 2024.

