## PROTOCOL

All patients will be trained preoperatively in pain assessment using a Numerical Rating Scale (NRS) from 0 (absence of pain) to 10 (maximum pain endured). All patients will receive the same anesthesia and analgesia protocol; fentanyl, propofol and rocuronium prior to intubation.

Anesthetic maintenance with 1 MAC of sevoflurane and boluses of muscle relaxant and fentanyl if there is an increase >20% in blood pressure or above baseline heart rate. The anesthetic protocol will include analgesia with 1 g of paracetamol and 50 mg of dexketoprofen every 8 hours and a bolus of 0.1 mg/kg of intravenous dexamethasone. When the patient reports an NRS > 3 and functional impact, intravenous morphine will be administered at a dose of 0.04 mg/kg every 10 minutes until NRS < 3 in the PACU and tramadol 1 mg/kg in the ward. The nursing staff and the anesthesiologist in charge of the PACU will be blind to the block received by the patient in each study group.

Before general anesthesia, patients will be assigned to one of the study groups depending on the anesthesiologist responsible for performing the blocks.

**SHAC + SSN Group (anterior approach):** with the patient in the supine position and the arm placed in abduction and slight external rotation the ultrasound probe will be positioned in the transverse axis between the coracoid process and the humeral head. After identifying the tendon of the subscapularis muscle, a puncture will be performed in a lateral to medial plane and the local anesthetic will be deposited at two levels; one deep to the subscapularis tendon at the pericapsular level of the glenohumeral joint (5 ml of ropivacaine 0.2%), and another in withdrawal at about the level of the fascia that separates the subscapularis and deltoid muscles at a more superficial level (10 ml of 0.2% ropivacaine). Subsequently, the ultrasound probe will be positioned in the transverse axis at level with the neck to locate the suprascapular nerve through an anterior approach as it ran beneath the omohyoid muscle. After hydrodissecting the correct plane with saline solution 5 ml of 0.2% ropivacaine will be administered, depositing the local anesthetic under the lower belly of the omohyoid muscle.

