## **VARIABLES EVALUATED**

The main variable will be the measurement of pain intensity according to the NRS at different times: preoperative and at the 1st, 2nd, 12th and 24th postoperative hours. As secondary variables, postoperative opioid requirements will be assessed in the form of intravenous morphine, measured in mg (only during the 2 hours of the patient's stay in the Postanesthesia Care Unit), and tramadol (mg) up to 24 hours postoperatively.

The degree of sensory block will be also assessed by a cold sensitivity test with a cotton swab dipped in cold water applied to the skin of the upper third of the arm, which will be graded with a sensitive scale going from 0 to 2 (2 being normal sensitivity to cold, 1 hypoesthesia and 0 anesthesia). The degree of motor block upon arrival at the PACU will be assessed by the movement of the arm using a simple numerical scale (0 = cannot raise the extended arm  $> 45^\circ$  and 1 = can raise the extended arm  $> 45^\circ$ ), the ease of performance of the corresponding anesthetic technique by the anesthesiologist using a simple verbal scale (easy/medium difficulty/difficult), the appearance of adverse effects (postoperative nausea and/or vomiting, hematoma, pruritus, urinary retention), the degree of patient satisfaction (very satisfied, satisfied or dissatisfied) and the notification of complications related to the anesthetic techniques performed.

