## **STATISTICAL ANALYSIS PLAN**

Continuous quantitative variables will be expressed as mean and standard deviation and the results will be contrasted using the Student's T test if normality criteria will be met, failing which they will be expressed as median and range and contrasted using the Mann Whitney's U. The qualitative variables will be expressed in absolute numbers and relative frequencies and the results of both groups will be contrasted using the Chi square. In addition, Fisher's test will be applied when necessary. Normality tests will be conducted for all continuous quantitative variables. The Kruskal-Wallis technique will be also employed with post-hoc application of the Bonferroni test for the analyses. The data will be processed using SPSS software version 19.0 (IBM Corporation, Armonk, NY, USA), assuming a p-value below 0.05 as significant.

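### Rescue opioids are dosed by body weight but compared in unadjusted milligrams between non-randomised groups, with weight not listed as a variable, so a weight imbalance can look like a difference in opioid use

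*Combined protocol and SAP*

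**What the plan says.** The Protocol section sets both rescue drugs per kilogram. In recovery, "intravenous morphine will be administered at a dose of 0.04 mg/kg every 10 minutes until NRS < 3 in the PACU"; afterwards, "tramadol 1 mg/kg in the ward".

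The Variables Evaluated section records the outcomes in absolute amounts: "postoperative opioid requirements will be assessed in the form of intravenous morphine, measured in mg" for the two hours in the recovery unit, and "tramadol (mg) up to 24 hours postoperatively". Body weight is not among the variables named there. The Goals section makes this the leading secondary objective: "Postoperative opioid consumption and comparison of total cumulative consumption between the two groups".

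On comparability of the groups, the Study Type section describes "An observational study of paired cohorts, not randomized" without naming a pairing variable, and the Protocol section states that "patients will be assigned to one of the study groups depending on the anesthesiologist responsible for performing the blocks".

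For continuous outcomes the Statistical Analysis Plan says "the results will be contrasted using the Student's T test if normality criteria will be met", with Mann-Whitney as the fallback. No covariate is mentioned.

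**The concern.** When each dose is a fixed amount per kilogram, the recorded milligrams are the product of how often rescue was given and how heavy the patient is. Only the first factor can be said to reflect the block. Two patients who trigger rescue equally often get different outcome values in proportion to their weights.

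Randomisation would make any weight imbalance a matter of chance. Here allocation follows the anesthesiologist, the pairing is undefined and the tests are unadjusted. Nothing in the plan secures weight balance, and since weight is not a listed variable, nothing in the plan provides for seeing an imbalance. What is at stake is the opioid comparison, for each drug taken separately. A rule for combining morphine and tramadol would not cure it. The main variable, the pain score, is not measured in milligrams and is not touched by this problem.

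**Working it through.** The plan has no figure of its own to reproduce: it gives no sample size calculation, weights or expected dose counts.

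**Inputs from the documents.** Morphine 0.04 mg/kg per bolus, repeated until the pain score target is met; tramadol 1 mg/kg; both outcomes in mg; unadjusted two-group tests at 0.05.

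**Inputs assumed.** Mean weight about 80 kg, coefficient of variation (CV) 18% (SD 0.18 × 80 = 14.4 kg), and a gap in mean weight between groups of 2 to 10 kg.

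**Step 1: one patient.** Recorded mg = number of doses × mg/kg per dose × weight.

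| Weight | One morphine bolus | Three boluses | One tramadol dose |
|---|---|---|---|
| 60 kg | 2.4 mg | 7.2 mg | 60 mg |
| 80 kg | 3.2 mg | 9.6 mg | 80 mg |
| 100 kg | 4.0 mg | 12.0 mg | 100 mg |

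For an equal number of doses, the ratio between 100 and 60 kg is 12.0/7.2 = 1.67. This compares two individuals, not two group means.

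**Step 2: group means, two models of need.**

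- *Number of doses independent of weight.* The spurious relative difference in mean mg is the gap divided by mean weight: 2/80 = 2.5% and 10/80 = 12.5%. On mg/kg it is zero.
- *Need fixed in mg.* A heavier patient reaches the target after fewer boluses. Apart from rounding to whole boluses, the spurious difference in mg is about zero. It then appears on mg/kg instead: for a 10 kg gap, 1 − 80/90 = 11% lower in the heavier group.

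**Step 3: false-positive rates with equal need in both groups** (simulated t tests, two-sided 0.05).

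- Weights 78 kg (SD 15), Poisson mean of 2 or 4 boluses independent of weight, 30 to 100 per group. On plain mg the rate was 0.05 to 0.06 with no gap, 0.06 to 0.13 with a 5 kg gap and 0.09 to 0.35 with a 10 kg gap. On mg/kg it was 0.04 to 0.06 throughout.
- Weights 80 kg (SD 14.4), Poisson mean of 1 or 3 boluses, 50 or 100 per group. On plain mg the rate was 0.04 to 0.06 at 2 kg, 0.05 to 0.10 at 5 kg and 0.07 to 0.27 at 10 kg.
- Weights 80 kg (SD 14.4), 10 kg gap, 50 or 100 per group, both models of need. Plain mg gave 0.18 to 0.29 if the bolus count is independent of weight. Mg/kg gave 0.07 to 0.11 if need is fixed in mg. Mg adjusted for weight gave about 0.05 to 0.06 under both.

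**Step 4: noise when weights are balanced.** If doses and weight are independent, squared CV of mg = (1 + CV_doses²)(1 + CV_weight²) − 1. With an assumed CV of doses of 0.80, this is 1.64 × 1.0324 − 1 = 0.693, against 0.640 for mg/kg: a ratio of 1.08. Patients with no rescue raise the CV of doses and shrink the ratio: 1.065 at a CV of 1.0 and 1.041 at 2.0. Across the first simulation's wider set of weight and dose assumptions, the inflation was about 4% to 25%.

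**The case against.** Four objections carry weight.

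1. **A reader might infer that weight is not collected.** The documents do not support that. Doses per kilogram cannot be given without a weight, and the Variables Evaluated section names no baseline variable at all, not even age or ASA class, which are entry criteria. The data questionnaire is not shown. What stands is that weight is not listed as a study variable or used in the analysis.

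2. **A reader might infer that mg/kg is the correct scale.** Morphine is titrated to a pain score, so if the amount needed for relief does not rise with weight, total mg is close to the right measure and mg/kg over-corrects. The documents do not say which model holds. This objection stands for morphine. It is weaker for tramadol, for which no titration is stated.

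3. **Large imbalances are not shown.** With SD 14.4 kg and an assumed 50 per group, the standard error of the difference in mean weight is 14.4 × √(2/50) = 2.9 kg, so a 10 kg gap is 10/2.9, or about 3.5 standard errors. That would take systematic selection, and nothing in the documents links the anesthesiologist to patient weight. This stands: 10 kg is the upper end of a range, not an expectation, and at 2 kg the false-positive rate is hardly affected.

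4. **This is one case of general unadjusted confounding.** True, but weight differs from other prognostic factors in that the protocol's own dosing rule builds it into the recorded outcome. That justifies a specific, small remedy even if wider adjustment is discussed separately.

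**Conclusion.** The point holds as a possible bias, not a demonstrated one. It needs two things together: a difference in mean weight between the groups, and a number of rescue doses that does not fall enough with weight to cancel it. The plan guards against neither.

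For an assumed gap of 2 to 10 kg around 80 kg, the false difference in mean mg runs from near zero (need fixed in mg) up to 2.5% to 12.5% (number of doses independent of weight). Tramadol is the more exposed drug. If weights are balanced, the cost is modest loss of precision and no bias.

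All sizes rest on assumed weights, dose counts and group sizes. The simulated error rates are for the t test, and they were not run for the Mann-Whitney fallback. The documents do not support the stronger conclusions that the opioid result will be biased or that most of the variation in mg reflects body size; in the simulations, the number of doses remained the main source of variation. Because the outcome is secondary, this is a minor-to-moderate improvement.

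**What to change.** - **Variables Evaluated:** list body weight as a study variable and report it by group.
- **Statistical Analysis Plan:** compare morphine mg and tramadol mg between groups with adjustment for body weight, for example by linear regression of mg on group and weight with robust standard errors. Prespecify mg/kg, or the number of rescue doses per patient, as a sensitivity analysis, and show unadjusted mg alongside so that the result can be set against reports in mg.

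Adjustment is preferable to a plain change of unit because it held the simulated error rate near 0.05 whether or not need depends on weight. Fixing the scale in advance also removes a choice between mg and mg/kg once the results are known.

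The cost is one data column, already needed to calculate the doses, and slightly more analysis. No dose or treatment changes.

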### **• Study population and total number of subjects.**

All patients consecutively scheduled for arthroscopic unilateral rotator cuff repair of the shoulder, who meet the inclusion criteria will be recruited for the study.

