## BACKGROUND AND JUSTIFICATION OF THE PROJECT

Arthroscopic shoulder surgery is related to a high incidence of postoperative pain, being rated as intense by 45% of patients in the immediate postoperative period (1). The management of these patients can be complex due to the high incidence of preoperative pain and its variability during the postoperative period, which is higher in patients undergoing rotator cuff repair surgery (2).

It is crucial to ensure adequate postoperative pain control in this type of intervention, especially in the context of major outpatient surgery. Adequate postoperative pain control can have several benefits, such as reducing hospital stay (3), accelerating postoperative rehabilitation (4), and improving long-term outcomes (5).

The PROSPECT guideline for rotator cuff repair surgery recommends associating a regional analgesic technique with a multimodal pharmacological approach to pain. (6).

Traditionally, the interscalene block has been considered the gold-standard for analgesia in shoulder surgery; However, its possible serious complications limit its use. Currently, most anesthesiologists choose to perform more distal peripheral nerve blocks of the brachial plexus (upper trunk block, supraclavicular block, infraclavicular block at the costoclavicular level, axillary nerve block...) which, although highly effective, continue to cause impairment. prolonged motor activity and are not free of complications (phrenic paralysis, transient nerve injuries, inadvertent vascular punctures...) (7).

Shoulder anterior capsular block (SHAC) has recently been described. It is a fascial block of the anterior capsule of the shoulder that aims to avoid motor impairment while maintaining optimal analgesic efficacy (8)(9). However, so far only anatomical and descriptive studies of small case series have been published. Therefore, this research work, with the objective of comparing the postoperative analgesic effectiveness of two regional analgesic techniques: the SHAC block associated with the suprascapular nerve block performed anteriorly vs. suprascapular and axillary nerve blocks performed posteriorly in operated patients. of the shoulder via arthroscopic procedures that cause intense postoperative pain.

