## **MATERIAL AND METHODS**

### **1.1 Definition of study subjects**

The inclusion criteria: being over 18 years of age, ASA physical status I – III and having been scheduled for shoulder arthroscopy surgery.

The exclusion criteria: any contraindication for performing regional anesthetic techniques (infection at the puncture point, alteration of hemostasis, allergy to local anesthetics, patient refusal to participate in the study, inability to evaluate postoperative pain, known neuropathy of the operated limb and patients who required conversion to open surgery).

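### Motor block is scored once, on PACU arrival, as absolute ability to raise the arm above 45°, with no preoperative test, so prior limitation that persists would count as motor block in this secondary comparison

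*Combined protocol and SAP*

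**What the plan says.** - **Measurement.** Under VARIABLES EVALUATED: "The degree of motor block upon arrival at the PACU will be assessed by the movement of the arm using a simple numerical scale". The scale has two values according to whether the patient "can raise the extended arm" above 45° (1) or not (0). It records ability at one postoperative moment, not a change.
- **Preoperative data.** Pain is the only variable with a preoperative time point. The sentence begins "The main variable will be the measurement of pain intensity according to the NRS at different times: preoperative and at the 1st" and goes on to the later hours. No preoperative test of arm elevation or strength appears anywhere.
- **Population.** The abstract recruits "All patients consecutively scheduled for arthroscopic unilateral rotator cuff repair of the shoulder". Section 1.1 admits shoulder arthroscopy more generally. The nearest exclusion is "known neuropathy of the operated limb", which does not cover limitation from a torn tendon, pain or stiffness.
- **Status.** Motor block is a secondary objective: "It will also evaluated the degree of sensory and motor block". The background says the SHAC block "aims to avoid motor impairment while maintaining optimal analgesic efficacy".
- **Allocation and analysis.** In the PROTOCOL section, "patients will be assigned to one of the study groups depending on the anesthesiologist responsible for performing the blocks". The statistical analysis plan compares qualitative variables by chi-square, or Fisher's test when necessary, with no baseline adjustment. The study type section speaks of paired cohorts but names no matching variable.

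**The concern.** A score of 0 on PACU arrival has two possible readings: the patient lost the ability to raise the arm, or never had it that day. With no preoperative record the two cannot be told apart, then or later. The operated structure helps to raise the arm, so prior limitation is plausible in this population.

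Two things are at stake. First, patients unable beforehand who remain unable score 0 under either technique, which pulls the two groups' rates together. Second, allocation follows the anesthesiologist, at two hospitals, so the share of such patients may differ between groups. The comparison could then be shifted in either direction, and the investigators would have no data with which to see or correct it. This is the only motor measurement in the plan, so any statement about motor sparing would rest on it.

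**Working it through.** The plan has no figure to reproduce: the sample-size section states that no calculation is performed, and no motor-block rate or rate of prior inability is given. What follows is illustrative.

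**Inputs, all assumed except the last**
- Block-caused inability: 20% in one group, 45% in the other.
- 50 patients per group.
- Share unable to raise the arm above 45° before the block, *q*: 0% to 40%, the same in both groups.
- Every prior inability persists to PACU arrival. This gives the largest dilution for a given *q*.
- Significance level 0.05 (statistical analysis plan), taken as two-sided because the plan does not say.

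**Formulas**
- Observed rate of score 0 = *q* + (1 − *q*)*p*, where *p* is the block-caused rate.
- The observed difference is therefore (1 − *q*) × 25 points.
- Power = Φ(difference/SE − 1.96), with SE = √{[*a*(1 − *a*) + *b*(1 − *b*)]/50} for observed rates *a* and *b*.

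**Worked case, *q* = 20%.** *a* = 0.20 + 0.80 × 0.20 = 0.36. *b* = 0.20 + 0.80 × 0.45 = 0.56. Difference 0.20. SE = √[(0.2304 + 0.2464)/50] = 0.0977. Power = Φ(2.048 − 1.96) = 54%.

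| Prior inability *q* | Observed rates | Difference (points) | Power as planned | Power among patients able before (*n* per group) |
|---|---|---|---|---|
| 0% | 20% vs 45% | 25 | 79% | 79% (50) |
| 2% | 21.6% vs 46.1% | 24.5 | 76% | 78% (49) |
| 5% | 24% vs 47.75% | 23.75 | 72% | 77% (47.5) |
| 10% | 28% vs 50.5% | 22.5 | 66% | 75% (45) |
| 20% | 36% vs 56% | 20 | 54% | 70% (40) |
| 30% | 44% vs 61.5% | 17.5 | 43% | 64% (35) |
| 40% | 52% vs 67% | 15 | 34% | 57% (30) |

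The last column uses 20% vs 45% with 50(1 − *q*) per group. Restricting loses patients but keeps the full 25-point difference, so power is higher at every *q* above zero.

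**Partial persistence.** If only half of prior inabilities persist, replace *q* by *q*/2. A prior rate of 20% then behaves like the 10% row (66%), and 40% like the 20% row (54%).

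**Imbalance with no true difference.** Assume block-caused inability of 30% in both groups, and prior inability of 10% in one and 25% in the other. Observed rates are 0.10 + 0.90 × 0.30 = 37% and 0.25 + 0.75 × 0.30 = 47.5%, a spurious gap of 10.5 points. At 50 per group, SE = 0.0982 and the gap reaches p < 0.05 about 19% of the time, against the nominal 5%.

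**The case against.** The documents report a high incidence of preoperative pain. They do not say that any patient cannot raise the arm, and give nothing on elevation or weakness. A reader might infer that a sizeable share is already unable, and that these patients must score 0 whatever block they receive. Neither is supported. Both techniques are analgesic and are given before surgery, so a patient limited by pain may raise the arm once blocked. The calculation assumes otherwise, and its results are therefore an upper bound. If prior inability is 2%, power drops by only about 3 points. This objection stands, and it is why no single figure can be given for the effect.

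A reader might also infer that a false difference is likely. The example needs an assumed 15-point imbalance and even then is significant in about one study in five. It is one instance of the general confounding that comes with allocation by anesthesiologist. What is specific here is that the relevant baseline variable is not recorded at all.

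Third, motor block is one of several secondary variables, and the study's stated objective is to compare analgesic effectiveness. Avoiding motor impairment is given as the aim of the SHAC technique, not as this study's main question. No endpoint has a power target, so lost power here defeats no planned conclusion. This limits the priority of the point but not its correctness.

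Finally, a baseline test does not isolate the block effect. The anesthetic protocol includes rocuronium, further relaxant and fentanyl. Residual relaxant or sedation, surgical pain and the repair itself can each stop a previously able patient from lifting the arm on arrival. This stands, and the outcome should be described accordingly.

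**Conclusion.** The point holds as a measurement weakness in one secondary outcome. As written, the score mixes prior inability with new inability. The neuropathy exclusion removes only one source of the former, and no later analysis can separate them without a preoperative record.

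The direction under equal prior inability is certain: the difference shrinks by the factor (1 − *q*) if inability persists. The size is not known. Under the assumed 20% vs 45% block rates and 50 per group, with full persistence, power ranges from 76% at 2% prior inability to 34% at 40%, against 79% with none. Unequal prior inability could bias the comparison either way.

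The documents do not support a claim that the primary pain comparison is affected, or that the motor result will be misleading. Priority is low to moderate; the case for acting rests on the low cost of the change.

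**What to change.** 1. Carry out the same 45° arm-raise test before the block, at the assessment where the preoperative NRS is recorded.
2. Report the number unable beforehand in each group.
3. Define the outcome as loss of ability (able before, unable on PACU arrival) and compare the groups among patients able before, using the chi-square or Fisher's test already planned.
4. State that residual relaxant or sedation, surgical pain and the repair itself can also cause inability on arrival, so the result is new inability and not purely block effect.

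**Cost.** A few seconds per patient at an assessment that already takes place, with no change to treatment. Patients unable at baseline leave this one secondary comparison. Under ETHICAL-LEGAL ASPECTS, changes to an approved protocol go back for re-evaluation, so the amendment must be submitted if approval has been given. For any patient already recruited, preoperative ability cannot be recovered, and this should be reported as a limitation.

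### The block complications named in the background are not solicited by name; they can be recorded only through an open notification item, so an absence of reports would be weak evidence in either group

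*Combined protocol and SAP*

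**What the plan says.** All references are to the combined protocol and SAP.

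- **BACKGROUND AND JUSTIFICATION OF THE PROJECT** says that current distal blocks are effective but carry complications, and names "phrenic paralysis, transient nerve injuries, inadvertent vascular punctures".
- **GOALS** (repeated in the ABSTRACT) makes complications a secondary objective: "the record of short-term complications (first 24 hours post-intervention): hematoma, pruritus, nausea and/or vomiting".
- **VARIABLES EVALUATED** gives a slightly longer list: "the appearance of adverse effects (postoperative nausea and/or vomiting, hematoma, pruritus, urinary retention". The same sentence ends with a further variable, "the notification of complications related to the anesthetic techniques performed". The section also scores motor block once, on PACU arrival, as able or unable to raise the extended arm beyond 45°.
- **PROTOCOL** assigns patients according to which anesthesiologist is responsible for the blocks, and blinds the PACU nurses and the PACU anesthesiologist. In the SHAC + SSN group the probe is placed "level with the neck to locate the suprascapular nerve through an anterior approach". The SSN + AN group is injected in the supraspinous fossa and at the quadrilateral space.
- **JUSTIFICATION OF SAMPLE SIZE** states no number of patients.

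**The concern.** A count of complications can be compared between groups only if both groups are asked the same question, in the same way, at the same time. Here the three complications that the protocol itself considers important depend on an item whose content, timing and reporter are not stated. The person best placed to see a vascular puncture is the operator, who knows the technique and on whom group membership depends. The blinded PACU staff are given no block complication to look for, and no neurological check at 24 h is listed.

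At stake is the complications comparison, which is one of several secondary outcomes. If few or no such events are reported, the result could be read as evidence that the blocks are safe, or equally safe, when it may reflect only how events were sought.

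**Working it through.** **Coverage.** The plan gives no event rate, power or sample size for complications, so there is no figure to reproduce. The check is a comparison of the sections.

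| Complication named in the background | On the objectives list? | On the VARIABLES EVALUATED list? | Other route |
|---|---|---|---|
| Phrenic paralysis | No | No | Open notification item |
| Transient nerve injury | No | No | Open notification item; motor score on PACU arrival only |
| Vascular puncture | No (hematoma is a partial proxy) | No (same) | Open notification item |

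None of the three is solicited by name. Of the four listed adverse effects, three (nausea/vomiting, pruritus, urinary retention) are typical opioid or anesthesia effects, and one (hematoma) is related to puncture or surgery. Urinary retention appears only in VARIABLES EVALUATED, so the two lists also disagree. A single yes/no motor score on PACU arrival cannot separate expected block from a residual deficit, and the cold test has no stated time.

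**How reporting affects the comparison.** Let p be the true rate and s the probability that an event is recorded. The expected recorded rate is s × p. The recorded ratio between groups is therefore (s₁/s₂) × (p₁/p₂). If one group had full recording and the other 50% (an illustration), equal true rates would appear as a twofold difference. The documents do not say which group would have the lower s.

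**What zero reports would mean.** With full recording, the exact one-sided 95% upper limit after 0 events in n patients is U = 1 − 0.05^(1/n). If a fraction s is recorded, the limit on the true rate is U/s. Both n and s = 0.5 are assumptions.

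| n per group (assumed) | U, full recording | U/0.5, half recorded |
|---|---|---|
| 25 | 1 − 0.05^(1/25) = 11.3% | 22.6% |
| 50 | 1 − 0.05^(1/50) = 5.8% | 11.6% |

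The middle column reflects small numbers alone. Only the step to the last column reflects incomplete recording.

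**What solicitation can and cannot achieve.** Take assumed true rates of 5% and 1%, two-sided alpha 0.05, and the normal approximation: power = Φ{(0.04√n − 1.96√(2 × 0.03 × 0.97)) / √(0.05 × 0.95 + 0.01 × 0.99)}. This gives 14.5% at n = 30, 21.4% at n = 50 and 38.1% at n = 100 per group. By the same approximation, 80% power would need about 285 per group. Better questions make the counts comparable; they do not make a study of this kind large enough for rare events.

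**The case against.** The strongest reply is that the plan does collect block complications. The sentence that lists the adverse effects goes on to a dedicated variable for complications of the techniques, and hematoma is itself related to puncture. That is right, and a reader who infers that block complications are left out goes too far: they are undefined and unsolicited, not absent.

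Three other strong readings also fail.

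- **That these complications are the reason for the study.** The background gives the project's aim as "with the objective of comparing the postoperative analgesic effectiveness of two regional analgesic techniques", and says of the SHAC block that it "aims to avoid motor impairment while maintaining optimal analgesic efficacy". Motor impairment is measured, though only once and as yes/no.
- **That reporting is purely spontaneous.** The CONFIDENTIALITY section refers to an electronic questionnaire whose items are not in the available text. It may contain prompts. What can be said is that the plan does not specify any.
- **That under-reporting favours the new technique because only that group is injected in the neck.** No section assigns a higher respiratory or vascular risk to the anterior route. The background attributes the complications to a family of blocks that includes the axillary nerve block, part of the comparator. The operator is unblinded in both groups.

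It can also be said that the RECRUITMENT section allows the reading that one anesthesiologist performs both techniques, which would weaken the link between group and reporting habit. The operator would still know the technique. Finally, the protocol nowhere says that it will conclude these complications are absent, so the caution about interpretation is preventive.

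What remains is that three complications named by the protocol have no stated definition, assessor, method or timing, in a design where reporting can differ by group.

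**Conclusion.** The concern holds for the secondary complications outcome. Phrenic paralysis, transient nerve injury and vascular puncture can be recorded only through an open item, and reporting may differ between groups because the operator is unblinded, group depends on the operator, and the injection sites differ. The direction of any resulting bias is not established. An absence of reports would be weak evidence: with 25 to 50 patients per group, zero events is compatible with rates up to 11.3% to 5.8% under full recording, and up to 22.6% to 11.6% if half are recorded. These figures rest on assumed group sizes and an assumed 50% ascertainment. The primary pain comparison is not affected. The change is worth making because it is cheap, not because the study fails without it.

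**What to change.** Add the same yes/no items to the existing form for both groups, at contacts already in the plan:

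1. **At the procedure, by the operator:** blood on aspiration or visible vascular puncture.
2. **In the PACU, by the blinded staff:** dyspnoea and, if saturation is routinely monitored (an assumption; the documents do not mention it), the lowest SpO2 as a recorded value.
3. **At the 24 h pain reading:** any new residual numbness or weakness.

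Use one complication list in the ABSTRACT, GOALS and VARIABLES EVALUATED, and settle whether urinary retention belongs on it. Keep the open item for anything unforeseen. State in the analysis plan that unsolicited reports will not be used to conclude that these complications are absent, and report any zero count with its upper confidence limit.

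The cost is four or five extra form items, with no imaging, extra visit or change to treatment, and probably more events reported in both groups. There are limits. Dyspnoea and SpO2 are indirect signs of phrenic paralysis, a yes at 24 h does not by itself separate a lingering block from nerve injury, the procedural item still relies on an unblinded operator, and rare events may still not separate the groups.
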